8.4.2 Analyses of Secondary Endpoints

The secondary endpoints for percent change and absolute change from baseline will be summarized for each scheduled visit. These secondary endpoint analyses will be repeated using change from parent EOS and percent change from parent EOS and summarized with descriptive statistics at each scheduled visit. All analyses will be performed separately for each of the ICOAS and IAAS analysis sets.

8.4.3 Analyses of Exploratory Endpoints

All analyses will be performed separately by SOC-controlled period and All-IP period.

Subject incidence of adjudicated CV endpoints and non-coronary revascularization will be summarized.

The percent change and change from baseline in laboratory based exploratory endpoints at each scheduled visit will be summarized. For continuous exploratory endpoints, treatment group summary statistics (number of subjects, mean, median, standard deviation or standard error, first and third quartiles, minimum, and maximum) at all scheduled visits will be calculated.

8.4.4 Analyses of Laboratory Measurements

Descriptive statistics will be provided for actual values and changes from baseline in each applicable laboratory parameter at each protocol-specified scheduled visit.

Laboratory analytes are provided in the protocol Table 7. Lab shift table using the CTCAE v4.03 **or later** grading will be used for the select analytes of interest, when applicable. Shift tables will be provided for the SOC-Controlled period and the All-IP period. The results will be based on the maximum (ie. worst) shift from parent baseline to the end of the SOC-Controlled period and from the parent baseline to end of the All-IP period, respectively.

In addition, CK and liver function test (LFT) abnormalities will be assessed by the incidence during the SOC-Controlled period and during the All-IP period:

- CK > 5 x ULN
- CK > 10 x ULN
- ALT or AST > 3 x ULN
- ALT or AST > 5 x ULN
- Total bilirubin > 2 x ULN
- (ALT or AST > 3 x ULN) and (Total bilirubin > 2 x ULN or INR > 1.5)

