7.1.1.7 Week 12 (\pm 7 Days)

- Vital signs: sitting blood pressure (BP), heart rate (HR)
- Review AEs/SAEs
- Review concomitant medications
- Blood draw for fasting lipids (\geq 9 hour fasting sample), ApoA1, ApoB, Lp(a), Vitamin E (sample drawn, testing by reflex when LDL-C is $<$ 25 mg/dL), and chemistry, hematology, HbA1c, Anti-AMG 145 antibodies
- HCV viral load (in subjects positive for HCV)
- Urine pregnancy
- Urinalysis
- Urine microalbumin
- Dispense IP quantity for at-home injections for subjects on AMG 145 + SOC
- IP reconciliation

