7.1.1.8 Week 24 Visit (\pm 7 Days)

- Vital signs: sitting blood pressure (BP), heart rate (HR)
- Review AEs/SAEs
- Review concomitant medications
- Blood draw for fasting lipids (\geq 9 hour fasting sample), ApoA1, ApoB, Lp(a), Vitamin E (sample drawn, testing by reflex when LDL-C is $<$ 25 mg/dL), chemistry, hematology, HbA1c, Anti-AMG 145 antibodies
- HCV viral load (in subjects positive for HCV)
- Urine pregnancy
- Urinalysis
- Dispense IP quantity for at-home injections for subjects on AMG 145 + SOC
- IP reconciliation

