7.1.1.14 Week 48 Visit (\pm 7 Days)

- Vital signs: sitting blood pressure (BP), heart rate (HR)
- Review AEs/SAEs
- Review concomitant medications
- Body weight
- Blood draw for fasting lipids (\geq 9 hour fasting sample), ApoA1, ApoB, Lp(a), Vitamin E (sample drawn, testing by reflex when LDL-C is $<$ 25 mg/dL), hsCRP, chemistry, hematology, HbA1c, Anti-AMG 145 antibodies, coagulation
- HCV viral load (in subjects positive for HCV)
- Urine pregnancy
- Urinalysis

- Urine microalbumin
- Train subject on self-injection of AMG 145 (for subjects randomized to SOC-alone in Year 1)
- Observe subject self- inject AMG 145 at study site for subjects randomized to SOC-alone in Year 1 (AMG 145 administration must occur after other procedures).
- Dispense IP quantity for at-home injections to subjects with previous experience of self-injection with AMG 145

7.1.1.15 Week 50 (\pm 7 Days)–Additional Procedures for Subjects Randomized to SOC–alone in Year 1 with no Previous Experience of Self-injection and Selects Q2W Regimen

- Vital signs: sitting blood pressure (BP), heart rate (HR)
- Review AEs/SAEs
- Review concomitant medications
- Train subject on self-injection of AMG 145
- Observe subject self- inject AMG 145 at study site (AMG 145 administration must occur after other procedures)

7.1.1.16 Week 52 (\pm 7 Days)–Additional Procedures for Subjects Randomized to SOC–alone in Year 1 with no Previous Experience of Self-injection

- Vital signs: sitting blood pressure (BP), heart rate (HR)
- Review AEs/SAEs
- Review concomitant medications
- Train subject on self-injection of AMG 145
- Observe subject self- inject AMG 145 at study site (AMG 145 administration must occur after other procedures)
- Dispense IP quantity for at-home injections for subjects on Q2W dosing only

7.1.1.17 Week 56 (\pm 7 Days)–Additional Procedures for Subjects Randomized to SOC–alone in Year 1 with no Previous Experience of Self-injection and Selects QM Regimen

- Vital signs: sitting blood pressure (BP), heart rate (HR)
- Review AEs/SAEs
- Review concomitant medications
- Train subject on self-injection of AMG 145
- Observe subject self- inject AMG 145 at study site (AMG 145 administration must occur after other procedures)

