7.1.1.26 Weeks 116, 128, or 140 (\pm 7 Days)

- Vital signs: sitting blood pressure (BP), heart rate (HR)
- Review AEs/SAEs
- Review concomitant medications
- Dispense IP quantity for at-home injections
- IP reconciliation

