7.1.1.27 Week 152 (\pm 7 Days)

- Vital signs: sitting blood pressure (BP), heart rate (HR)
- Physical exam
- Body weight
- Review AEs/SAEs
- Review concomitant medications
- Blood draw for fasting lipids (\geq 9 hour fasting sample), chemistry, hematology, anti-AMG 145 antibodies, HbA1c, coagulation
- Urine pregnancy test
- HCV Viral load (in subjects positive for HCV)
- IP reconciliation

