Appendix A. Schedule of Assessments

Applies to both AMG 145 and SOC-alone groups unless specified otherwise					
Timepoint/Frequency	W116	W128	W140	W152	EOS Phone visit W156
General Procedures					
Vital Signs (sitting BP, HR)	X	X	X	X	
Review for AEs/SAEs	X	X	X	X	X
Concomitant therapy	X	X	X	X	X
Physical Exam				X	
Body Weight				X	
Laboratory					
Fasting lipids				X	
Chemistry, fasting glucose				X	
Hematology				X	
Coagulation (PT/INR)				X	
HbA1c				X	
Anti-AMG 145 antibodies				X	
HCV viral load ^l				X	
Urine pregnancy				X	
Investigational Product					
IP Dispense	X	X	X		
IP Reconcile	X	X	X	X	

Page 3 of 3

^a D1 = day of first administration of IP. This visit should also coincide with EOS visit for parent study; for visit windows see [Section 7](#) of the protocol. Procedures NOT conducted as part of EOS visit for parent study should be completed at this visit.

^b Training visit applies to subjects who are randomized to AMG 145 and select the Q2W regimen

^c Training visit applies to subjects who are randomized to AMG 145 and select QM regimen

^d Only if enrollment into 138 exceeds last laboratory visit from parent study by 30 days. Cardiac History Form will also need to be completed.

^e Telephone visit for subjects randomized to SOC-alone

^f Only for subjects receiving AMG 145 who have selected the QM regimen

^g Only for subjects receiving AMG 145 who have selected the Q2W regimen

^h Vitamin E samples will be drawn for all applicable visits, testing will be conducted by reflex when LDL-C is < 25 mg/dL

ⁱ Training visit applies to subjects who are randomized SOC-alone in year 1 and select the Q2W regimen in year 2

^j Training visit applies to subjects who are randomized SOC-alone in year 1 and select the QM regimen in year 2

^k Only for subjects randomized to placebo or SOC in parent study AND randomized to SOC-alone in Year 1

^l HCV antibodies only in high risk subjects (see [Section 7.1.2.4](#)) or if ALT or AST > 2x ULN; viral load only in subjects positive for HCV

^m FSH in applicable subjects for study entry only – see [exclusion criteria](#); urine pregnancy in females of childbearing potential

ⁿ Dispense IP for at-home injections (only for subjects who have previous experience of self-injecting AMG 145)

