Sex

For subjects that enroll in an extension study, the subject's sex is the sex recorded on the extension study eCRF. For other subjects, the subject's sex is the sex recorded on the parent study eCRF.

Race

For subjects that enroll in an extension study, the subject's race is the race recorded on the extension study eCRF. For other subjects, the subject's race is the race recorded on the parent study eCRF.

Country and Region

For subjects that enroll in an extension study, the subject's country and region are those recorded in the extension study. For other subjects, the subject's country and region are those recorded in the parent study.

Baseline Metabolic Syndrome

For each subject without type 2 diabetes mellitus, metabolic syndrome is identified by the presence of 3 or more of the components listed below (modified AHA/NHLBI criteria). Subjects with type 2 diabetes cannot be categorized as having metabolic syndrome.

Risk Factor	Defining Level
Elevated waist circumference:	
Non-Asian:	
Men	≥ 102 cm
Women	≥ 88 cm
Asian:	
Men	≥ 90 cm
Women	≥ 80 cm
Triglycerides	≥ 150 mg/dL
HDL cholesterol	
Men	< 40 mg/dL
Women	< 50 mg/dL
Blood pressure	SBP ≥ 130 mmHg or DBP ≥ 85 mmHg OR Hypertension checked 'yes' on CV Medical History eCRF
Fasting glucose	≥ 100 mg/dL

4-Level Treatment Group

All tables in this interim analysis will be summarized by randomized group (AMG 145+SOC vs. SOC alone). Since subjects received either AMG 145 or control treatment in parent study, the tables will be further categorized using the following 4 levels (parent study treatment group/current study treatment group): "AMG 145/AMG 145 + SOC"; "AMG 145/SOC Only"; "Control/AMG 145 + SOC", and "Control/SOC Only".

6. Analysis Subsets

Interim SOC-Controlled period Analysis Set

The Interim SOC-**C**ontrolled period **A**nalysis **S**et (ICOAS) will include all subjects randomized in this study who have at least 12 weeks of potential follow-up (eg. subjects for whom Data Cutoff Date - Study Date for Study Day 1 + 1 > 91 days); the restriction on potential follow-up is to prevent operational bias that may occur by the increased frequency of visits during the first 12 weeks of the study. Subjects will be analyzed according to the treatment group to which they were randomized during the SOC-Controlled period. All data from the SOC-Controlled period will be summarized, regardless of possible IP discontinuation.

Interim All-IP period Analysis Set

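### CK and liver abnormality incidence in the All-IP period is counted over 5 scheduled chemistry draws in Control/SOC Only and 4 in the other groups, with no per-visit rate to show it

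*SAP*

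**What the plan says.** SAP 8.4.4 plans threshold categories for CK, ALT or AST, total bilirubin and the combined liver criterion. The rule is that "CK and liver function test (LFT) abnormalities will be assessed by the incidence during the SOC-Controlled period and during the All-IP period". The laboratory shift tables in the same section use the worst shift from parent baseline to the end of each period. Actual values and changes are summarized by scheduled visit, but the threshold categories are not.

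SAP 5.3 (4-Level Treatment Group) adds that "the tables will be further categorized using the following 4 levels", formed from parent-study and current treatment: AMG 145/AMG 145 + SOC, AMG 145/SOC Only, Control/AMG 145 + SOC and Control/SOC Only.

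In the protocol, Section 7.1.1.19 and Appendix A schedule chemistry at Week 60 under footnote k: "Only for subjects randomized to placebo or SOC in parent study AND randomized to SOC-alone in Year 1". The SAP's own window tables (SAP Appendix A) likewise give Week 60 chemistry only to SOC subjects who had control in the parent study.

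Under SAP 5.1, the SOC-Controlled period of a subject dosed at Week 48 ends the day before that dose, and All-IP starts the next day. SAP Appendix A opens the Week 48 laboratory window at the start of All-IP.

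**The concern.** The chance that a subject is ever counted as abnormal in a period rises with the number of times blood is drawn, unless an abnormality, once present, is still there at the next draw. If one of four groups shown side by side has an additional draw, its percentage can be higher with no difference in risk. The affected group is the one starting AMG 145 for the first time at Week 48, where a reader would look for a new CK or liver signal.

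The SAP already accepts the principle for the randomized period: Section 6 requires 12 weeks of potential follow-up in the SOC-Controlled set, to avoid bias from more frequent early visits. It has no counterpart for laboratory looks in All-IP.

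**Working it through.** The documents give no figure for draw counts or for CK/LFT incidence, so there is no plan figure to reproduce on this point.

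**Step 1: scheduled chemistry after Day 1.** Protocol 7.1.1.7 to 7.1.1.27 and Appendix A list Weeks 12, 24, 48, 84, 104 and 152 for all subjects (for example "hsCRP, chemistry, hematology, HbA1c, Anti-AMG 145 antibodies, coagulation" at Week 48), plus Week 60 under footnote k. The SAP windows after Week 24 are Weeks 48, 72, 96 and 104, plus Week 60 for parent-control subjects on SOC.

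**Step 2: draws per SAP period**, for subjects dosed on the Week 48 visit day with full follow-up:

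| Source | SOC-Controlled | All-IP, three groups | All-IP, Control/SOC Only |
|---|---|---|---|
| Current protocol | 2 (W12, W24) | 4 (W48, W84, W104, W152) | 5 (plus W60) |
| SAP windows | 2 (W12, W24) | 4 (W48, W72, W96, W104) | 5 (plus W60) |

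The 5-against-4 split therefore holds on either schedule. At a cutoff after Week 60 and before the next shared draw (Week 84 in the current protocol, Week 72 in the SAP windows), it is 2 (W48, W60) against 1 (W48).

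**Step 3: effect of an extra look.** Let p be the chance of an abnormality at one draw and k the number of draws. With independent draws, period incidence is 1 − (1 − p)^k. With weight w on perfectly persistent abnormalities, it is w·p + (1 − w)·[1 − (1 − p)^k]. The documents give no p. I assume 0.5% and vary it.

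At p = 0.5%, independent draws:
- k = 1: 0.50%
- k = 2: 1 − 0.995² = 1.00%
- k = 4: 1 − 0.995⁴ = 1.99%
- k = 5: 1 − 0.995⁵ = 2.48%

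Control/SOC Only against the other groups, full follow-up:
- w = 0: 2.48/1.99, ratio 1.25. Over p = 0.2% to 2% the ratio is 1.24 to 1.25.
- w = 0.5: (0.25 + 0.5 × 2.48)/(0.25 + 0.5 × 1.99) = 1.49/1.24, ratio 1.20.
- w = 1: 0.5/0.5, ratio 1.0.

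At the early cutoff (2 against 1):
- w = 0: 1.00/0.50, ratio about 2.0.
- w = 0.5: (0.25 + 0.5 × 1.00)/0.50 = 0.75/0.50, ratio 1.5.
- w = 1: ratio 1.0.

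**Step 4: All-IP against SOC-Controlled.** For 4 against 2 draws at p = 0.5%, the ratio is 1.99/1.00, about 2, or 1.24/0.75, about 1.66, at w = 0.5. All-IP is also longer. Draws per year (52.18 weeks) on the current protocol are 2/48 × 52.18 = 2.17 in SOC-Controlled and 4/108 × 52.18 = 1.93 in All-IP, counted to Week 156. Much of that gap is therefore longer follow-up, which any cumulative incidence reflects.

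**The case against.** The strongest reply is that this is a descriptive interim plan, that Week 60 falls after the randomized period, and that laboratory values are already summarized by visit with the number of subjects. Those facts are right, and they limit the point. They do not answer it, because by-visit summaries of values contain no threshold rates, and the four-group split puts the unequally sampled group beside the others.

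Leaving out Week 60 would also discard the first scheduled on-drug chemistry in Control/SOC Only. That stands, and it is why a version without Week 60 should supplement the planned table and not replace it.

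A reader might infer four stronger things.

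- **Incidence will appear to fall over the years.** On the current protocol, shared draws do thin from three (Weeks 12, 24, 48) to two (Weeks 84, 104) to one (Week 152). But 8.4.4 reports two periods, not years, and no per-patient-year laboratory rate is planned. The SAP cites Amendment 2 and has no Year 3 window; the third year came with Amendment 5.
- **All-IP must exceed SOC-Controlled.** This does not follow. All-IP stops at the data cutoff, so some subjects may have only one or two draws, and persistence shrinks the effect.
- **The randomized comparison is distorted.** Week 60 cannot do this, and Weeks 12 and 24 are scheduled alike in both arms. One matter is open: protocol 7.1.1.14 lists on-site Week 48 dosing only for SOC-alone. If an AMG 145 + SOC subject doses a day or more after the visit, the period dates leave that subject's Week 48 draw in SOC-Controlled. The documents do not settle how often this happens.
- **Laboratory-related adverse events follow the same pattern.** Adverse events are also reviewed at visits without chemistry, and protocol 9.1.2 says abnormal findings without clinical significance should generally not be recorded as events.

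**Conclusion.** The point holds as a limited one. In the four-group All-IP tables, Control/SOC Only has one scheduled chemistry draw more than the other groups, and neither the incidence nor the worst shift takes account of it. With full follow-up the excess from the extra look alone is up to about 1.25-fold (2.5% against 2.0% at an assumed 0.5% per independent draw), about 1.2-fold with half persistence and none with full persistence. At an early cutoff the relative excess can be larger, on smaller percentages.

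The counts assume dosing on the Week 48 visit day, and that the protocol's parent-study placebo or SOC subjects are the SAP's parent-control group. The All-IP and SOC-Controlled percentages should not be read against each other, because both the number of looks and the length of follow-up differ. This is an inexpensive improvement to the safety tables and does not challenge the randomized comparison.

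**What to change.** In SAP 8.4.4:

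1. Keep the period incidence, and add each CK/LFT category as subjects abnormal divided by subjects tested at each scheduled visit.
2. State the number of scheduled chemistry draws per group and period, including the period to which the Week 48 draw is assigned.
3. In the four-group All-IP tables, add a version of the incidence and worst shift without the Week 60 draw, beside the planned one.
4. Base any statement over time on visits shared by all groups, with windows updated to the current protocol. Week 84 is nominally Day 7 × 84 + 1 = 589, which the SAP labels Week 96. Week 152 is Day 7 × 152 + 1 = 1065, which falls in the open-ended Week 104 window.

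The cost is SAP wording and additional table layouts, with no new data. The version without Week 60 loses the first on-drug sample in one group, and per-visit rates miss abnormalities seen only at unscheduled draws, so the planned tables stay.

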5.1 Study Time Points

Baseline

For variables other than sex, race, country, region, and baseline metabolic syndrome, baseline is defined as the parent study baseline. Note that baseline metabolic syndrome will be using parent study baseline information, but with updated sex and race from the extension study data.

First Dose Date

For subjects randomized to AMG 145+SOC, the first dose date is the first date at which the subject was administered IP. For subjects randomized to SOC, the first dose date is the first date at which the subject was administered IP at or after the Week 48 clinical visit.

End of Investigational Product (EOIP) Date

If a subject has completed or discontinued IP, the EOIP date is the date recorded on the final IP dose date eCRF.

End of Study (EOS) Date

For each subject, the End of Study Date is the date recorded on the End of Study eCRF.

Enrollment Date

The enrollment date for a subject is either the subject's EOS date for the parent study or the date that subject has signed the ICF for Study 20120138, whichever is later.

Randomization Date

The randomization date for each subject is the date the investigator (or designee) confirms in the IVRS that the subject has met all eligibility criteria and is randomized.

Study Day 1

For subjects randomized to AMG 145+SOC arm and received at least one dose of AMG 145, Study Day 1 is defined as the first day that AMG 145 is administered during this study.

For subjects randomized to SOC only arm, or randomized to AMG 145+SOC arm but never received AMG 145, Study Day 1 is defined as the day of randomization.

Study Day

For each subject, and for a given study visit date, study day is defined as the number of days since Study Day 1:

$$\text{Study day} = (\text{study visit date} - \text{Study Day 1 date}) + 1$$

If the date of interest is prior to the Study Day 1:

$$\text{Study day} = (\text{study visit date} - \text{Study Day 1 date})$$

SOC-Controlled period

The start of the SOC-Controlled period is Study Day 1.

For the end of the SOC-Controlled period:

- If a subject is administered a dose of IP at Week 48, the day prior to the week 48 IP date is the end of the SOC-Controlled period.
- If a subject is not administered a dose of IP at Week 48, the SOC-Controlled period will end the earliest of Study Day 343, the EOS date, or data cutoff date.

All-IP period

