The Interim All-IP period Analysis Set (IAAS) will include all subjects that were randomized **in this study** and dosed with IP and on-study in the All-IP period. Data will be summarized analyzed from the start of the All-IP period to EOS or the data cutoff, whichever occurs first.

7. Data Screening and Acceptance

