8.1 General Principles

Statistical analyses in this open-label extension study will be descriptive. Subject disposition, demographics and baseline characteristics will be summarized.

Summary statistics for continuous variables will include the number of subjects, mean, median, standard deviation or standard error, first and third quartiles, minimum, and maximum. For categorical variables, the frequency and percentage will be given.

All analyses will be carried out separately for the ICOAS and the IAAS analysis sets unless specified otherwise. There will be no imputation for missing data. Deaths and major cardiovascular events from this and other phase 3 studies will be adjudicated by an independent Clinical Events Committee (CEC) to facilitate aggregated analyses across the program. These events adjudicated by the CEC include:

- death by any cause
- cardiovascular death
- myocardial infarction
- hospitalization for unstable angina
- coronary revascularization
- stroke
- hospitalization for heart failure
- transient ischemic attack (TIA)

In addition, non-coronary revascularizations will be collected.

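### The All-IP incidence of CK and liver abnormalities has no stated denominator and counts pre-dose Week 48 samples of SOC-alone subjects as on-drug data, while on-drug sampling differs between the SOC-alone columns by schedule alone

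*SAP*

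**What the plan says.** SAP 8.4.4 lists six CK and liver-function thresholds and states that these "abnormalities will be assessed by the incidence during the SOC-Controlled period and during the All-IP period". It gives no denominator and no rule for a subject without a sample.

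The default is in SAP 8.1: "All analyses will be carried out separately for the ICOAS and the IAAS analysis sets unless specified otherwise". SAP Section 6 admits to the IAAS every randomized subject "dosed with IP and on-study in the All-IP period". The ICOAS, by contrast, takes only subjects "who have at least 12 weeks of potential follow-up". On missing values, SAP 8.1 says "There will be no imputation for missing data".

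For a subject dosed at Week 48, SAP 5.1 says that "the day prior to the week 48 IP date is the end of the SOC-Controlled period"; the All-IP period starts the next day, which is the dose date itself. SAP Appendix A opens the Week 48 chemistry window at the beginning of the All-IP period.

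Protocol 7.1.1.14 has SOC-alone subjects inject at the Week 48 visit after the other procedures, which include the blood draw. Chemistry at Week 60 is restricted by Protocol Appendix A, footnote k: "Only for subjects randomized to placebo or SOC in parent study AND randomized to SOC-alone in Year 1". All other subjects next have chemistry at Week 84 in the protocol, and at Week 72 in the SAP windows. The SAP cites Amendment 2; the protocol supplied is Amendment 6.

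**The concern.** A CK or transaminase abnormality can be found only when blood is drawn. A subject enters the All-IP set on one dose, but the first on-drug chemistry of a SOC-alone subject comes 12 to 36 weeks after that dose. The interim cutoff is not fixed, so some SOC-alone subjects will have been dosed without yet having an on-drug result. Meanwhile their pre-dose Week 48 result sits in the All-IP period by date.

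The SOC-alone columns of an on-drug safety table would then mix off-drug results with subjects not yet sampled on drug. SAP 5.3 reports Control/SOC Only and AMG 145/SOC Only as separate columns, and only the first has the Week 60 draw. A difference between them could come from the blood-draw schedule rather than from the drug. SAP Section 1 says that the tables support regulatory filings.

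**Working it through.** **Plan's own figures.** The plan gives no figure for All-IP laboratory incidence. Its only precision figures, the adverse-event intervals in Protocol 10.2, reproduce: 3478 + 950 = 4428, split 2:1 into 1476 and 2952. Exact limits are 3.96% to 6.25% for 74/1476 and 4.25% to 5.86% for 148/2952, which round to the stated limits. They do not bear on this point beyond confirming the 2:1 split.

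**Step 1: where the Week 48 sample falls.** Let D be the Week 48 dose date. The SOC-Controlled period ends on D − 1 and the All-IP period starts on D, so a sample drawn on D is All-IP.

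| Group (parent/current) | Week 48 sample when dosed on the visit day | Weeks to next scheduled chemistry |
|---|---|---|
| Control/SOC Only | All-IP by date, off drug | 60 − 48 = 12 |
| AMG 145/SOC Only | All-IP by date, off drug | 72 − 48 = 24 (SAP) or 84 − 48 = 36 (protocol) |
| Both AMG 145 + SOC groups | All-IP by date, on drug after about 48 weeks of IP | 24 (SAP) or 36 (protocol) |

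An AMG 145 + SOC subject who takes the Week 48 dose at home on a later day has the sample in the SOC-Controlled period instead.

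**Step 2: contrast with the ICOAS.** Its rule is more than 91 days. The Week 12 visit is nominally on day 7 × 12 + 1 = 85, and its window closes on day 92. Whatever its purpose (the SAP gives operational bias from visit frequency), the rule covers the first chemistry draw. The IAAS has no counterpart.

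**Step 3: share with an on-drug sample after the Week 48 dose.** Assumption: follow-up after that dose at cutoff is uniform on 0 to F weeks. For a gap of g weeks, share = max(0, 1 − g/F).

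| F (weeks) | Control/SOC Only, g = 12 | Others, SAP, g = 24 | Others, protocol, g = 36 |
|---|---|---|---|
| 24 | 50% | 0% | 0% |
| 36 | 67% | 33% | 0% |
| 48 | 75% | 50% | 25% |
| 56 | 79% | 57% | 36% |

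At F = 48 the ratio between the two SOC-alone columns is 75/50 = 1.5 on the SAP schedule and 75/25 = 3 on the protocol schedule.

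**Step 4: by arm and overall, F = 48.** The parent-study control share c is not given; assume 1/3 to 1/2, and 2:1 retained in the IAAS.

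- SOC-alone arm, 0.75c + s(1 − c): 58% to 62.5% with s = 0.50 (SAP); 42% to 50% with s = 0.25 (protocol).
- Whole IAAS, post-dose samples only, 0.75(c/3) + s(1 − c/3): 53% to 54% (SAP); 31% to 33% (protocol).
- Whole IAAS, with the Week 48 sample of every AMG 145 + SOC subject credited, 2/3 + (SOC-alone share)/3: 86% to 87.5% (SAP); 81% to 83% (protocol).

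**Step 5: direction in a SOC-alone column.** Let q be the proportion abnormal on the pre-dose sample, p the proportion abnormal among those sampled on drug, and s the share sampled on drug. Ignoring overlap, the reported incidence over the IAAS is about q + s·p. It exceeds p when q > (1 − s)p. At F = 48 that means q > 0.25p for Control/SOC Only, and q > 0.50p (SAP) or 0.75p (protocol) for AMG 145/SOC Only. The error can go either way.

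**The case against.** A reader might infer that most dosed subjects are never sampled on treatment in the All-IP period, so that the incidence is simply diluted and AMG 145 looks safer than it is. The documents do not support that. About two thirds of subjects are AMG 145 + SOC. If they dose on the Week 48 visit day, their Week 48 sample is on treatment and inside the period. The pre-dose results in the other arm can push the figure up as well as down.

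It can also be said that no text counts an unsampled subject as free of abnormality. SAP 8.1 rules out imputation, and where missing is to count as an outcome the protocol says so: Protocol 10.4.2.3 counts missing LDL-C as failure to reach the target. This stands. The IAAS denominator is inferred from SAP 8.1, not stated in 8.4.4. But if the inference is wrong, the denominator is undefined. The usual alternative, subjects with any value in the period, would not help: a SOC-alone subject qualifies on the pre-dose Week 48 sample.

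There is some mitigation. The analyses are descriptive. Visit summaries show the number of subjects, missing-data patterns are summarized for selected endpoints, and exposure is reported by group. These help a careful reader but do not correct the incidence table.

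**Conclusion.** The plan is wrong as written here. Its period and window rules put off-drug samples of SOC-alone subjects into an on-drug safety incidence, and neither 8.4.4 nor the IAAS definition ensures that a counted subject has an on-drug sample. This part follows from the text without any assumption about the cutoff.

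The size does depend on assumptions. With follow-up uniform on 0 to 48 weeks, on-drug ascertainment differs 1.5-fold (SAP windows) to 3-fold (current protocol) between Control/SOC Only and AMG 145/SOC Only. The threefold figure needs both the Week 84 schedule and that cutoff, so it should not be read as the expected size. A later cutoff narrows the gap, and unscheduled retests would add samples. The AMG 145 + SOC columns are much less affected, and the net direction of bias is not determined.

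**What to change.** In SAP 5.1, 8.4.4 and Appendix A:

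1. Assign laboratory samples drawn on or before the Week 48 dose to the SOC-Controlled period in both arms. Move the Week 48 window to match; otherwise the Week 24 window, which runs to the end of the SOC-Controlled period, would absorb these samples. Without the reassignment, rule 2 would drop a same-day pre-dose sample from both periods.
2. Count All-IP CK and liver abnormalities only on samples after the first All-IP dose. Use as denominator the IAAS subjects with at least one such sample, and print that number beside the IAAS number for each of the four groups.
3. Apply the matching rule in the SOC-Controlled period: at least one sample after Study Day 1.
4. Reconcile the Week 72 and Week 84 chemistry schedules between SAP and protocol.

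No new data are needed. The cost is smaller All-IP denominators and less precise percentages: in the F = 48 illustration, 53% to 54% of the IAAS on the SAP schedule or 31% to 33% on the protocol schedule. The AMG 145 + SOC arm also gives up its Week 48 sample to the SOC-Controlled table. Sampled subjects will still differ in number of draws because of Week 60, so a footnote should say so.
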